## **2.3 Tertiary Objective**

The tertiary objective is to identify psychosocial correlates of adherence changes in AYA with KT and SB. Using validated surveys, we will examine perceived barriers, self-efficacy and healthcare responsibility before and after the 6-month intervention and follow-up periods. Hypothesis 3: Positive change in adherence behavior is associated with positive changes in self-efficacy, reduced perceived barriers and increased healthcare responsibility.

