### 6.3 Tertiary Endpoints

The tertiary endpoint is to identify psychosocial correlates of adherence changes in AYA with KT and SB. We hypothesize that improved treatment adherence from baseline to intervention

---

---

end will be mediated by increases in self-efficacy and healthcare responsibility and declines in perceived barriers, but will not be related to knowledge gained. We also hypothesize that we will observe greater changes in self-efficacy in Arm 2 vs. Arm 1 because of the specifically targeted text messages that emphasize people's progress and ability to perform difficult behavior. For this Aim, all participants will complete the baseline survey measures of self-efficacy, healthcare responsibility, perceived barriers and knowledge again at the end of the 6-month intervention via WTH. The **independent variables** in the analyses for Aim 3 are: 1) change in self-efficacy score 2) change in healthcare responsibility score 3) change in perceived barriers and 4) change in knowledge score from baseline to end of intervention. The **dependent variable**, or primary outcome measure, is: change in the *proportion of weeks with adherence behavior performance  $\geq 85\%$  prescribed/expected between baseline (run-in period) and intervention period*. A secondary analysis will examine usage of the educational modules viewed in the WTH portal. Usage will be tracked as yes/no and time spent. We hypothesize that increased usage will associate with increased knowledge but will have no effect on increased treatment adherence. Prior research supports the hypothesis that increased knowledge is not sufficient to promote positive health behavior.

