#### 6.5 Statistical Methods

Clinical and demographic variables will be compared with chi-square or two-sample t-tests for parametric and Fisher's exact or Wilcoxon rank-sum tests for non-parametric data. Treatment groups will be compared with similar analyses to confirm equity in randomization. We will compare change over time in % adherence between arms by fitting quasi-least squares (QLS) and generalized estimating equation (GEE) longitudinal models. The QLS/GEE models include a regression model for the primary outcome variable, in addition to a separate model for the correlation amongst the repeated measures on each subject. The AR (1) correlation structure is plausible because it forces a decline between measures with increasing separation in time; however, we will assess the sensitivity of results to choice of structure. In addition, the models will include treatment group and a time by treatment group interaction. If the interaction term differs significantly from zero, this will indicate that the change over time differs significantly between treatment groups. All analyses will follow the intention-to-treat principle. We will analyze the results for each disease group (SB, KT) separately, although the overall analytical models are the same.

Analysis for Aim 1 and Aim 2 will utilize GEE/QLS models to compare the change over time in the outcome between arms.

For Aim 3, Pearson's or Spearman's Correlations will be calculated to observe the association between outcome and each independent variable.

The statistical analysis will follow the intention-to-treat principle.

---

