## 6.6 Sample Size and Power

The disease groups (KT or SB) will be analyzed separately in the primary analysis. We assume 180 KT and 180 SB recipients will complete the study, allowing for 10% drop-outs. With 90 participants per arm per disease group, setting alpha at 0.05, we will have >90% power to detect a medium effect size of 0.5 in timing change in proportion of timing adherence, using a two group t-test (based on TAKE-IT). Based on preliminary data from TAKE IT and published studies, it is reasonable to expect an average of 8% improvement in timing adherence when a behavioral economics model with financial incentives is applied. An effect size of 0.50 would be observed if the difference in average improvement was 8% between groups, while the standard deviation of post minus pre improvement was 16. With 90 subjects per arm, the detectable effect size is also 0.50 for Aim 2. For Aim 3, a 0.050 two-sided Fisher's z test of the null hypothesis that the Pearson correlation coefficient is 0 will have 82% power to detect a correlation of 0.300 when the sample size is 90.

Table 3. Anticipated Participant Enrollment				
	Year 1	Year2	Year 3	Year 4 *
Expected Participant Recruitment (Cohort 1 and 2)	100	100	100	100
Expected Parent Recruitment (Cohort 3)	200	200	200	200
Anticipated drop-outs (10%)	30	30	30	30
Anticipated cumulative n by end of study year	270	540	810	1080

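### Aim 3 hypothesises mediation but plans only simple correlations, and the plan does not say whether these are pooled over arms, run within arm or adjusted for arm

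*Combined protocol and SAP*

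**What the plan says.** Section 6.3 (Tertiary Endpoints) predicts that the improvement in adherence from baseline to the end of the intervention "will be mediated by increases in self-efficacy and healthcare responsibility and declines in perceived barriers, but will not be related to knowledge gained". It adds: "We also hypothesize that we will observe greater changes in self-efficacy in Arm 2 vs. Arm 1". It gives no size for that difference and predicts no arm difference in responsibility, barriers or knowledge.

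Objective 2.3 puts the same hypothesis more weakly: "Positive change in adherence behavior is associated with positive changes in self-efficacy, reduced perceived barriers and increased healthcare responsibility".

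Section 6.5 (Statistical Methods) gives the whole Aim 3 method in one sentence: "For Aim 3, Pearson's or Spearman's Correlations will be calculated to observe the association between outcome and each independent variable". It assigns the GEE/QLS models to Aims 1 and 2 and says that the two disease groups are analysed separately. For Aim 3 it names no arm term, partial correlation or mediation model, and no test of the predicted self-efficacy difference between arms.

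Section 6.6 (Sample Size and Power) bases Aim 3 on "a 0.050 two-sided Fisher's z test of the null hypothesis that the Pearson correlation coefficient is 0", with 82% power for r = 0.300 at n = 90. The same paragraph gives 90 as the number per arm per disease group.

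**The concern.** There are two separate gaps.

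**Hypothesis and method do not match.** To show that a psychosocial change mediates the intervention's effect, one needs the effect of arm on the mediator and the effect of the mediator on adherence given arm. A simple correlation estimates neither. Section 1.1 lists mechanisms of behaviour change among the study's aims, so a reader of the results may take a significant correlation as support for the mechanism stated in 6.3.

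**The handling of arm is unspecified.** If the correlation is taken over both arms, assignment is a common cause of both variables wherever the intervention moves both. The protocol expects this for self-efficacy: Arm 2 combines payments tied to the 85% adherence target with tailored texts, and 6.3 attributes the self-efficacy gain to the texts. The payments could raise adherence while the texts raise self-efficacy, so that the two correlate across arms with no link between them within an arm.

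**Working it through.** **Step 1. Reproduce the stated power (6.6).** Fisher's z, two-sided 0.05: power = Φ(atanh(r)·√(n−3) − 1.96), plus a negligible opposite tail. With r = 0.300, atanh(r) = 0.3095.

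- n = 90: 0.3095 × √87 = 2.887; Φ(0.927) = 82.3%. This matches the stated 82%.
- n = 180: 0.3095 × √177 = 4.118; Φ(2.158) = 98.5%.

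The stated figure is therefore correct for 90 participants. That equals one arm of one disease group; both arms of a disease group give 2 × 90 = 180.

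**Step 2. Can either reading test mediation?** A within-arm correlation contains no arm contrast, so it says nothing about whether the intervention moved the mediator. A pooled correlation mixes the arm differences with the within-arm association and separates neither. The mismatch with 6.3 holds on both readings.

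**Step 3. Size of the arm-induced correlation, if arms are pooled.**

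Inputs:
- Adherence shift d_y = 8/16 = 0.50 SD, from 6.6 ("An effect size of 0.50 would be observed if the difference in average improvement was 8% between groups", with an SD of 16).
- Self-efficacy shift d_x: not in the documents; assumed 0.2 to 0.5 SD.
- Within-arm correlation zero, 1:1 allocation, normal variables with equal variance.

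Formula: r = (d_x·d_y/4) / √[(1 + d_x²/4)(1 + d_y²/4)].

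Example, d_x = d_y = 0.5: 0.0625/1.0625 = 0.059. At n = 180, 0.0589 × √177 = 0.783, and Φ(−1.177) + Φ(−2.743) = 12.3%.

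| Assumed d_x | Induced r | P(p<0.05), n = 180 | P(p<0.05), n = 90 in total |
|---|---|---|---|
| 0 | 0 | 5.0% | 5.0% |
| 0.2 | 0.024 | 6.2% | 5.6% |
| 0.3 | 0.036 | 7.7% | 6.3% |
| 0.5 | 0.059 | 12.3% | 8.5% |

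Simulation with 20,000 trials per setting agreed: 5.9%, 8.0% and 12.2% at n = 180 for the last three rows.

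**Step 4. With arm partialled out.** In the same simulations the partial correlation given arm reached p<0.05 in 4.9% to 5.1% of trials for d_x from 0.2 to 0.5. Power for r = 0.300 uses √(n−4): 0.3095 × √176 = 4.106, and Φ(2.146) = 98.4% at n = 180, against 98.5% unadjusted. At n = 90 it is 81.9%, against 82.3%.

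**The case against.** **Pooling is not stated.** A reader might infer that the correlations will run over both arms, because 6.3 has all participants completing the surveys and the only split named in 6.5 is by disease group. The documents do not support this as fact. The survey sentence describes data collection, and n = 90 fits a within-arm analysis exactly. On that reading arm cannot confound and the rate stays at 5%. This objection stands, so the inflation is conditional on pooling.

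**Only one of four variables is affected as predicted.** A reader might extend the argument to all the psychosocial correlates. Section 6.3 predicts an arm difference for self-efficacy alone, so the argument reaches no further on the protocol's own expectations.

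**The effect is small.** A reader might suppose a serious inflation by letting both variables shift by much more than 0.5 SD. That would exceed the protocol's own 0.50 for adherence, and the protocol gives no figure for self-efficacy. An induced r of at most 0.06 over the assumed range is small beside the 0.300 planned for.

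**Strictly, it is not type I error.** The null hypothesis in 6.6 is a correlation of zero, and under pooling the correlation really is slightly above zero. This is correct: the fault lies in reading the result as a psychosocial link.

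**The word may be loose.** Objective 2.3 and the method sentence in 6.5 both speak of association, and correlations suit that. This shows that a wording change could close the gap. It does not remove the contradiction with 6.3.

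**Conclusion.** The mismatch between the mediation hypothesis in 6.3 and the correlations in 6.5 holds however the arms are handled. The plan also leaves that handling open, and n = 90 sits unexplained beside the 180 expected per disease group.

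The inflation is secondary and modest: about 6% to 12% instead of 5% at n = 180, and about 5.5% to 8.5% at n = 90. It applies only to self-efficacy and only if arms are pooled. It rests on an assumed self-efficacy shift and no within-arm association. It also carries over to the Aim 3 outcome (proportion of weeks at or above 85%) the 0.50 that 6.6 plans for change in timing adherence. The figures are for Pearson's correlation with normal data; Spearman's was not computed.

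This is a tertiary aim, and the between-arm comparisons of Aims 1 and 2 are unaffected. The change is worth making because it is nearly free.

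**What to change.** 1. In 6.5, replace the raw Aim 3 correlations by a regression of adherence change on each survey change score, adjusted for arm (or the partial correlation given arm), using both arms of each disease group.
2. In 6.6, restate the Aim 3 power for n = 180: about 98% for r = 0.300 if all 180 have usable surveys at both times. If a within-arm analysis is intended, say so and keep n = 90.
3. In 6.3, either change the mediation wording to association, in line with objective 2.3, or pre-specify an indirect effect (arm to mediator, times mediator to adherence given arm) with a bootstrap confidence interval. Label that estimate exploratory: the mediator is measured at the end of the period over which adherence accrues, so temporal order is not established.

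The cost is a few sentences in the plan and slightly more analysis of data already being collected. Arm adjustment takes about 0.1 percentage point of power at n = 180.

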## 6.6 Sample Size and Power

The disease groups (KT or SB) will be analyzed separately in the primary analysis. We assume 180 KT and 180 SB recipients will complete the study, allowing for 10% drop-outs. With 90 participants per arm per disease group, setting alpha at 0.05, we will have >90% power to detect a medium effect size of 0.5 in timing change in proportion of timing adherence, using a two group t-test (based on TAKE-IT). Based on preliminary data from TAKE IT and published studies, it is reasonable to expect an average of 8% improvement in timing adherence when a behavioral economics model with financial incentives is applied. An effect size of 0.50 would be observed if the difference in average improvement was 8% between groups, while the standard deviation of post minus pre improvement was 16. With 90 subjects per arm, the detectable effect size is also 0.50 for Aim 2. For Aim 3, a 0.050 two-sided Fisher's z test of the null hypothesis that the Pearson correlation coefficient is 0 will have 82% power to detect a correlation of 0.300 when the sample size is 90.

Table 3. Anticipated Participant Enrollment				
	Year 1	Year2	Year 3	Year 4 *
Expected Participant Recruitment (Cohort 1 and 2)	100	100	100	100
Expected Parent Recruitment (Cohort 3)	200	200	200	200
Anticipated drop-outs (10%)	30	30	30	30
Anticipated cumulative n by end of study year	270	540	810	1080

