## 6 STATISTICAL CONSIDERATIONS

### 6.1 Primary Endpoint

The primary endpoint for this pilot clinical trial is to compare the efficacy of two 6-month mhealth-based interventions to promote treatment adherence among AYA with KT or SB.

The **independent variable** in the analyses for Aim 1 is *exposure to feedback + incentive* (intervention, Arm 2). The **dependent variable**, or primary outcome measure, is: change in the *proportion of weeks with adherence behavior  $\geq 85\%$  expected between baseline (run-in period) and intervention period*. Weekly adherence proportions will be calculated by observing the number of non-missed/late treatment episodes over the total number of episodes in that week.

The outcome will then be the proportion of weeks with treatment adherence  $\geq 85\%$ . Participants who do not submit the correct number of pictures within the prescribed window of their expected time due for treatment will be counted as nonadherent for that episode of med taking/cathing. Over the study period, changes in weekly timing adherence will be assessed as a repeated measure over time. In secondary analysis, we will examine variability in inter-dose intervals (based on time-stamping of photos) to account for doses that are taken beyond the time window.

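### The >90% power in 6.6 rests on timing-adherence inputs; nothing in the document supports an effect size of 0.5 for the weeks-at-85% outcome that 6.1 names as primary

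*Combined protocol and SAP*

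**What the plan says.** Section 6.1 scores each week by the share of treatment episodes that were neither missed nor late, and then cuts that score: "The outcome will then be the proportion of weeks with treatment adherence" at or above 85%. The primary measure is the change in this proportion between run-in and intervention. Section 6.3 uses the same measure as the dependent variable for Aim 3 ("proportion of weeks with adherence behavior performance" of at least 85%). Section 6.1 adds that "changes in weekly timing adherence will be assessed as a repeated measure over time", which carries no cut.

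Two other sections describe the outcome without the 85% threshold. Section 2.1 states the primary outcome as change in the share of time that a participant is adherent. Section 6.5 says "We will compare change over time in % adherence between arms", and that "the models will include treatment group and a time by treatment group interaction".

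Section 6.6 states that "we will have >90% power to detect a medium effect size of 0.5 in timing change in proportion of timing adherence", using a two-group t-test with 90 per arm per disease group and alpha 0.05. Its support is that "it is reasonable to expect an average of 8% improvement in timing adherence", and that 0.5 follows from an 8% difference between groups if "the standard deviation of post minus pre improvement was 16". The sentence giving the SD names no measure. It directly follows the timing-adherence sentence and reuses its 8%, so timing adherence is the natural reading.

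Elsewhere the 85% figure appears only as the Arm 2 payment target (3.1.2, 3.1.3, 4.3.1, 4.3.2, 8.7). No section gives an expected value, a difference or an SD for the proportion of weeks reaching it.

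**The concern.** A mean and SD for a weekly score do not determine the mean and SD of the same score once it has been cut at 85% and counted over weeks. The baseline makes this sharper. The run-in lasts two weeks (3.1.2, 3.3.1), so on the weeks scale a participant's baseline can take only three values: 0, 50 or 100%. An SD of 16 points for the change from such a baseline is possible but cannot be taken for granted.

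At stake is whether the one power figure given for Aim 1 applies to the outcome that 6.1 calls primary. The two disease groups are analysed separately, so the question arises twice.

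**Working it through.** **1. The plan's own figure.** Inputs from 6.6: difference 8, SD 16, n = 90 per arm, alpha 0.05 (sidedness of the t-test not stated; two-sided assumed).

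- Effect size d = 8/16 = 0.50.
- Noncentrality = d × √(n/2) = 0.50 × √45 = 3.35, with 178 degrees of freedom.
- Power = 91.6% (noncentral t), or 91.8% by the normal approximation.

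The stated >90% is reproduced. Since only d enters, any outcome with a true d of 0.5 has this power under the t-test.

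**2. What d = 0.5 requires on another scale.** The difference must be half the SD: 8 points at SD 16, but 15 points at SD 30. For exactly 90% power, d = 0.4858, so the detectable difference is 0.4858 × SD:

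| Assumed SD (points) | 16 | 20 | 25 | 30 | 35 |
|---|---|---|---|---|---|
| Difference for 90% power (points) | 7.8 | 9.7 | 12.1 | 14.6 | 17.0 |

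**3. Could the weeks-scale SD be 16?** This step is an illustration; the document gives no inputs for it. Assume 2 run-in weeks, 26 intervention weeks (6 months), weeks independent given the person, and no true change. Sampling noise alone then gives

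SD = 100 × √( E[p(1−p)] × (1/2 + 1/26) ),

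where p is the chance that a week reaches 85%.

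| Assumption about p | SD of change (points) |
|---|---|
| Beta(0.1, 0.1): most people nearly always or nearly never adherent; E[p(1−p)] = 0.0417 | 15.0 |
| 5% (or 95%) for everyone | 16.0 |
| 10% (or 90%) for everyone | 22.0 |
| Beta(0.5, 0.5); E[p(1−p)] = 0.125 | 25.9 |
| 20% (or 80%) for everyone | 29.4 |
| 30% (or 70%) for everyone | 33.6 |
| 50% for everyone | 36.7 |

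The run-in supplies (1/2)/(1/2 + 1/26) = 93% of this noise variance. Real differences between people in how much they change would add to it. So 16 can be reached, but only near the low end of these cases.

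**4. Power on the weeks scale.** Two-group t-test, 90 per arm, two-sided 0.05; differences and SDs assumed:

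| Difference | SD 25 | SD 30 | SD 35 |
|---|---|---|---|
| 8 points | 57% | 43% | 33% |
| 12 points | 89% | 76% | 63% |
| 16 points | 99% | 95% | 86% |

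Power runs from well below the stated figure to above it, depending on two numbers that the plan does not give. Power under the GEE/QLS model of 6.5 was not computed, because the coding of time is not stated.

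**The case against.** The strongest reply is that 6.6 states power for a standardised effect, that 8% and 16 are only an example of how 0.5 could arise, and that 0.5 has the stated power on any scale. The last part is correct, and the arithmetic stands. But 6.6 offers those two numbers as the reason to regard 0.5 as realistic, and gives no other. On the weeks scale that reason is missing.

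A second reply is that timing adherence is not foreign to the primary outcome: 6.1 builds the weekly score from on-time episodes and follows it as a repeated measure, and 2.1 and 6.5 use uncut wording. This also stands in part. It means that 6.1 cannot simply be declared the right definition and the others loose phrasing, since 2.1 states its own version outright. It does not supply a difference or SD for the weeks outcome.

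A reader might go further and infer that the trial is underpowered. The documents do not support that. The SD on the weeks scale may well exceed 16, but the difference may also exceed 8 points, not least because Arm 2 is paid for reaching 85%. A reader might also infer that a null result would be uninterpretable. That is too strong: its confidence interval would still show which differences are excluded, whatever the planning power was.

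**Conclusion.** The point holds as a gap between the power statement and the named outcome. The >90% is correct for an effect size of 0.5, and its stated support concerns timing adherence. It is not shown to apply to change in the proportion of weeks at or above 85%, and four sections do not agree on which measure is primary. No corrected power figure can be given from the documents. Under the assumptions in the working, noise alone puts the change-score SD anywhere from about 15 to 37 points. At SDs of 25 to 35, power is 33% to 57% for 8 points and 86% to 99% for 16 points. These ranges show how much depends on the missing inputs; they do not estimate this trial's power.

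**What to change.** Before analysis, make 2.1, 6.1, 6.5 and 6.6 name one primary outcome, by either route:

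- **(a) Keep the proportion of weeks at or above 85%.** Bring 2.1 and 6.5 into line with 6.1. In 6.6, replace the >90% statement with the power, or the detectable difference at 90 per arm, over a labelled range of differences and SDs that reflects the two-week baseline. The two-group t-test is an acceptable planning approximation.
- **(b) Make change in mean timing adherence primary.** The 6.6 inputs then apply as they stand, and the proportion of weeks at or above 85% becomes secondary. Sections 2.1, 6.1, 6.3 and 6.5 need matching wording.

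The cost of (a) is that the stated power may become a range or look less favourable. The cost of (b) is that the measure now in 6.1 loses its primary status. Neither needs extra participants.

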## 7 SAFETY MANAGEMENT

### 7.1 Clinical Adverse Events

Clinical adverse events (AEs) will be monitored throughout the study.

### 7.2 Adverse Event Reporting

Since the study procedures are not greater than minimal risk, SAEs are not expected. If any unanticipated problems related to the research involving risks to subjects or others happen during the course of this study (including SAEs) these will be reported to the IRB in accordance with CHOP IRB SOP 408: Unanticipated Problems Involving Risks to Subjects. AEs that are not serious but that are notable and could involve risks to subjects will be summarized in narrative or other format and submitted to the IRB at the time of continuing review. The Data Safety Management Board (DSMB) will review all adverse events.

This study supports and encourages bi-directional messaging. Because of this capability, study participants may reveal sensitive and serious thoughts or feelings, such as the desire to kill oneself, the occurrence of a serious medical incident requiring immediate medical attention

---

and other possibilities. While we expect events like this to be rare, we have implemented the following protocol to ensure these events are handled efficiently and effectively.

1. Study personnel will review participant-derived messages daily.
2. If a participant reaches out without the portal prompting him/her, an incident report is generated and sent to the site's research coordinator and the team project managers (DCC personnel).
3. Relying site coordinators are responsible for monitoring and addressing their site's incident reports and messages between normal working hours (0800-1700) Mondays through Fridays. The DCC is responsible for monitoring and addressing any incident reports and messages at all other times outside of the window mentioned.
4. If the content of the message (whether sent when prompted, reviewed in step 1, or sent when not prompted) indicates a serious adverse event, the coordinator who discovered the message will first contact the DCC PI, [name].
5. [name] will decide how to proceed. Options include, but are not limited to, contacting the local treatment team, the team psychologist or an emergency response team.
6. If the coordinator cannot reach [name], the coordinator will contact the DCC psychologist, [name].

A list of emergency contacts, including national hotlines for suicide prevention, child abuse support and more, is available to all study team members, and is attached to the eIRB application in section 12. Study personnel are instructed to have a low-threshold for contacting emergency response teams.

